7.1.5. Pharmacokinetics

Samples for determination of concentrations of imlifidase in serum will be taken at the times presented in the study flow charts (Table 1, Table 2, Table 3 and Table 4). The actual date and time of collection of each sample will be recorded in the eCRF. Samples will be analyzed by a validated electrochemiluminescence based immunoassay using the MSD technology. Full details of the analytical method used, and the analysis results will be detailed in a separate bioanalytical report.

7.1.6. Immunogenicity

Samples for the determination of ADA IgE and ADA IgG levels in serum will be taken at the times presented in the study flow charts (Table 1, Table 2, Table 3 and Table 4). The date and time of collection of each sample will be recorded in the eCRF. Samples will be analysed for anti-implifidase IgE and IgG, using a customized validated imlifidase ImmunoCAP test. Full details of the analytical method used, and the analysis results will be detailed in a separate bioanalytical report.

7.2. Safety Assessments related to Endpoints

7.2.1. Safety Laboratory

The following blood samples will be taken at screening and time points specified in flow charts, Table 1, Table 2, Table 3 and Table 4. Other samples may be taken at the investigator's discretion.

Table 5: Safety laboratory tests

Clinical chemistry*	Hematology	Coagulation
P-IgG	B-Hemoglobin	PT (INR)
P-Alkaline phosphatase (ALP)	B-Differential analysis of leucocytes	P-APTT
P-Alanine aminotransferase (ALT)	B-Thrombocytes	
P-Aspartate aminotransferase (AST)		
P-Bilirubin, total		
P-Glucose		

Table 5: Safety laboratory tests

Clinical chemistry*	Hematology	Coagulation
P-Sodium		
P-CRP		
P-Albumin		
P-Urea		
P-Triglycerides		
P-Creatinine		
P-Creatinine phosphokinase		

* May be taken as serum samples if that is standard procedure at the local lab

7.2.2. Physical Examination

A complete physical examination will be performed at time points indicated in the study flow charts ([Table 1](#) and [Table 3](#)) and include an assessment of the following: general appearance, head and neck, lymph nodes, abdomen, musculo-skeletal, cardiovascular, respiratory and gross neurological examination. The physical examination shall be performed by an investigator.

7.2.3. Vital Signs

Blood pressure, pulse rate, respiratory frequency and body temperature will be measured at time points indicated in the study flowchart ([Table 1](#), [Table 2](#), [Table 3](#) and [Table 4](#)).

Systolic and diastolic blood pressure will be measured after the subject has been in supine position for at least 5 minutes. All recordings will be performed using validated standard equipment. Clinically significant abnormal findings will be reported as AEs.

7.2.4. ECG

ECG, according to standard procedure at the clinic, will be taken after 10 minutes' rest at time points indicated in the study flowchart ([Table 1](#) and [Table 3](#)). Additional ECGs may be performed by the Investigator for safety reasons.

The Investigator or designee will evaluate whether the ECG is normal or abnormal and whether it is clinically significant, if abnormal. Clinically significant abnormal findings will be reported as AEs.

7.2.5. Adverse Events

AEs will be recorded during the study period, from obtaining the informed consent to the end of study. For further information on definitions and reporting of AEs, see [Section 9](#).

7.3. Other Assessments

7.3.1. Demographics and Baseline Data

Information about gender, race, age at inclusion, weight and height will be collected at the screening visit for each subject. Measurements should be taken without shoes. Medical history will be recorded at screening.

7.3.2. Pregnancy Test

Serum β -hCG will be determined for all female subjects at screening, and at the end of study visit, using validated standard methods.

ONLY FOR AUSTRIA; in accordance with Austrian Medicinal Products Act, women of childbearing potential must perform a pregnancy test monthly during the study. At timepoints with no scheduled study visit, a pregnancy test in urine may be performed at home and result checked at the following visit.

7.3.3. Concomitant medication and other treatments

Concomitant medication and other treatments (including PE) will be recorded throughout the study.

7.3.4. Analysis of SARS-CoV-2 virus

PCR testing for SARS-CoV-2 virus will be performed at screening.

8. BIOLOGICAL SAMPLING PROCEDURES

8.1. Handling, Storage and Destruction of Biological Samples

Safety samples will be disposed after analyses according to local laboratory practice.

Biological blood samples collected for central analysis may be stored by the sponsor for a maximum of 5 years after completion of the study report.

Details on handling of biological samples are described in the laboratory manual that will be provided to the site prior to inclusion of the first subject.

8.2. Chain of Custody of Biological Samples

A full chain of custody is maintained for all samples throughout their life cycle.

The principal investigator keeps full traceability of collected biological samples from the subjects while in storage at the centre until shipment and keeps documentation of receipt of arrival.

The sample receiver keeps full traceability of the samples while in storage and during use until used or disposed.

Hansa Biopharma keeps oversight of the entire life cycle through internal procedures, monitoring of study sites and auditing of external laboratory providers.

8.3. Withdrawal of Informed Consent for Biological Samples

If a subject withdraws consent to the use of biological samples, the samples will be disposed/destroyed, if not already analysed and documented.

The principal investigator:

- Will ensure that subject withdrawal of informed consent is notified immediately to Hansa Biopharma.
- Will ensure that biological samples from that subject, if stored at the study site, are immediately identified, disposed/destroyed and the action documented.
- Will ensure the local laboratory(ies) holding the samples is/are informed about the withdrawn consent immediately and that samples are disposed/destroyed, and the action documented returned to the study site.

Hansa Biopharma ensures the central laboratory(ies) holding the samples is/are informed about the withdrawn consent immediately and that samples are disposed/destroyed, and the action documented returned to the study site.

In the event that analysis/research has already been performed, Hansa Biopharma will retain the results and associated data for regulatory reasons, but these will not be used in any subsequent analyses.

9. ADVERSE EVENTS AND SERIOUS ADVERSE EVENTS

9.1. Definitions

9.1.1. Adverse event

An AE is the development of an undesirable medical condition or the deterioration of a pre-existing medical condition following or during exposure to a pharmaceutical product, whether or not considered causally related to the product. Relationship to the study drug will be deemed as not related, unlikely, possible or probable. An undesirable medical condition can be symptoms (e.g., nausea and chest pain), signs (e.g., tachycardia and enlarged liver) or the abnormal results of an investigation (e.g., laboratory findings and ECGs).

In cases of surgical or diagnostic procedures, the condition/illness leading to such a procedure is considered as the AE rather than the procedure itself.

In case of a fatality, the cause of death is considered as the AE, and the death is considered as its outcome.

9.1.2. Serious adverse event

An SAE is an AE or suspected adverse reaction (SAR) that is considered "serious" if, in the view of either the investigator or Hansa Biopharma, it results in any of the following outcomes:

- Results in death
- Is immediately life-threatening
- Requires in-patient hospitalisation or prolongation of existing hospitalisation
- Results in persistent or significant disability or incapacity
- Is a congenital abnormality or birth defect
- Is an important medical event that may jeopardise the subject or may require medical intervention to prevent one of the outcomes listed above. Examples of such events include allergic bronchospasm requiring intensive treatment in an emergency room or at home, blood dyscrasias or convulsions that do not result in inpatient hospitalization, or the development of drug dependency or drug abuse.

Life-threatening event: An AE or suspected adverse reaction is considered "life-threatening" if, in the view of either the investigator or Hansa Biopharma, its occurrence places the subject or subject at immediate risk of death. It does not include an AE or suspected adverse reaction that, had it occurred in a more severe form, might have caused death.

Disability is defined as a substantial disruption in a person's ability to conduct normal life functions.

Hospitalisation: Admittance to an emergency room for observation without being admitted to the hospital may be considered to be an AE but is not considered as an SAE. However, complications that occur during hospitalization are AEs, and if a complication prolongs hospitalization, the event is considered serious.

9.2. Collection and Recording of Adverse Events

In clinical studies, an AE/SAE can occur at any time after signing of the informed consent until the end of the study, including run-in or washout periods, even if no study treatment has been administered, e.g., an AE can be related to a procedure in the protocol.

AEs will therefore be collected on the AE CRF from the time of signing of the informed consent and throughout the study including the follow-up period.

AEs can be collected by:

- The subject's response to questions about his/her health (a standard non-leading question such as "Have you had any health problems since you were last asked/your last visit?")
- Symptoms spontaneously reported by the subject
- Investigations and examinations where the findings are assessed by the investigator to be clinically significant changes or abnormalities
- Other information relating to the subject's health becoming known to the investigator (e.g. hospitalisation)

9.2.1. Variables

The following variables will be recorded in the CRF for each AE; description of the AE, the date and time (if applicable) when the AE started and stopped, severity based on Common Terminology Criteria for AEs grading (CTCAE v.4.03) whether the AE is serious or not, causality assessment, action taken and outcome.

9.2.1.1. Causality Assessment

For each reported AE, the investigator will make an assessment of the relationship of the event to study procedures and/or IMP using the following criteria.

- **Unrelated:** applicable to an AE that occurs when the subject was not exposed to study treatment or another cause is obvious.
- **Unlikely to be related:** applicable to an AE that meets the following criteria
 - Does not follow a reasonable temporal sequence from study drug dosing
 - May readily have been produced by the subject's clinical state, environmental, or toxic factors, or other therapy administered to the subject
- **Possibly related:** applicable to AEs where connection with dosing of study drug appears unlikely but cannot be ruled out. Applicable to AEs where:

- It follows a reasonable temporal sequence dosing with study drug
- It follows a known pattern of response to study drug dosing (based on animal studies)
- **Probably related:** applicable to AEs that are considered, with a high degree of certainty, to be related to the study drug. Applicable to AEs where
 - It follows a reasonable temporal sequence study drug dosing
 - It cannot be reasonably explained by the known characteristics of the subject's clinical state, environmental or toxic factors, or other modes of therapy
 - It follows a known pattern of response to study drug dosing (based on animal studies).
- For SAEs, causal relationship will also be assessed for any study procedure.

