As for all biologics, there is a risk of infusion reactions associated with imlifidase treatment. Three non-serious and one serious infusion related reactions regarded as related to treatment have occurred in 114 subjects receiving imlifidase. Signs and symptoms associated with infusion related reactions included, but were not limited to dyspnoea, pharyngeal oedema, sinus tachycardia, chest discomfort and flushing. To mitigate the risk of infusion related reactions, all subjects receive glucocorticoid and antihistamine treatment prior to dosing and are closely monitored during the infusions.

In vitro studies have revealed that imlifidase cleaves biologics originating from rabbit and human IgG including; thymoglobulin, IVIg, basiliximab, alemtuzumab, rituximab, adalimumab, denosumab, belatacept and etanercept. The optimal interval between imlifidase administration and these biologics has not been tested (2018-003R).

The rationale for the 3-day window between imlifidase and IVIg dosing is aimed to prevent cleavage of the IVIg based on the pharmacokinetic and pharmacodynamic profiles of imlifidase. In one of the clinical studies (14-HMedIdeS-04), alemtuzumab was given four days post dosing of imlifidase and in one clinical study (15-HMedIdeS-06), IVIg was given seven days post dosing of imlifidase.

Adverse events after administration of IVIg do occur but are seldom serious. There is a very small risk of anaphylaxis, often in subjects with severe IgA deficiency. Other reported side effects include headache, myalgia, transient hypotension and flushing (all of which can be corrected by slowing the infusion rate), meningism, aseptic meningitis, skin reactions (especially eczema), neutropenia, worsening of renal failure, and thromboembolic events (DVT, MI and stroke) attributable to hyperviscosity ([Hughes et al. 2014](#)).

As an extra safety measure for women of child bearing potential, the requirement for highly effective contraception is part of the inclusion criteria for this study. Additionally, a pregnancy test will be performed at the screening visit to ensure the patient is not pregnant.

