9.2.6. Reporting of Suspected Unexpected Serious Adverse Reactions

SUSARs must be reported to RAs. A suspected serious adverse reaction is any SAE for which there is a reasonable possibility that the investigational product caused the AE. A serious adverse reaction is considered "unexpected" if it is not listed in the reference safety information section of the investigator brochure or is not listed at the specificity or severity that has been observed.

SUSARs with an outcome of death or which are life threatening must be reported to the relevant RAs within 7 calendar days, all other SUSARs must be submitted within 15 calendar days. The SUSAR reporting procedures are detailed in the study Safety Management Plan. This plan is an agreement between Hansa Biopharma and Primevigilance. Hansa Biopharma will notify the appropriate RA(s) and all participating study investigators of any SUSARs on an expedited basis and in accordance with applicable regulations. In addition, Hansa Biopharma is

responsible for informing all investigators in all other ongoing studies involving imlifidase about all SUSARs.

It is the responsibility of the site investigator to promptly notify the IEC/IRB and other appropriate institutional regulatory bodies of all SUSARs received involving risk to human subjects as per their applicable requirements.

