4.7.1 Adverse events

Adverse events (AEs) will be classified according to the latest effective version of MedDRA.

A treatment emergent adverse event (TEAE) is any adverse event occurring after the administration of the IMP and within the time of residual drug effect, or a pre-treatment adverse event or pre-existing medical condition that worsens in intensity after administration of the IMP and within the time of residual drug effect.

The time of residual drug effect is the estimated period after the administration of the IMP, where the effect of the product is still considered to be present based on pharmacokinetic, pharmacodynamic or other substance characteristics. The residual drug effect is generally accepted to be 5 times the terminal half-life. The terminal half-life of imlifidase is expected to be within the range of approx. 100 hours, i.e. in this study the residual drug effect is likely to be well within the 29 Day assessments. All AEs occurring up to Day 29 are regarded as treatment emergent.

An AE overview summary table will be prepared including the number of patients reporting an AE, the percentage of patients (%) with an AE, and the number of events (E) reported for the following categories:

- TEAEs
- Related TEAEs (TEAEs considered to be possibly or probably related to IMP as judged by the investigator)
- Related Serious TEAEs
- Deaths
- Treatment-emergent Serious Adverse Events (SAEs)
- TEAEs leading to withdrawal
- Severe and life-threatening AEs

Treatment-emergent AEs will be summarised in a table by dictionary level, i.e., System Organ Class (SOC) and Preferred Term (PT) for MedDRA. The table will display the total number of patients reporting a TEAE, the percentage of patients (%) with a TEAE and the number of events (E) reported. TEAEs will be presented by SOC sorted alphabetically and PT sorted in decreasing frequency of occurrence. For the summary tables the SAF set will be applied.

Summary tables will be prepared for:

- All TEAEs
- TEAEs by causality (related/unrelated)
- TEAEs by intensity
- Related TEAEs by intensity
- SAEs
- SAEs by causality (related/unrelated)
- Treatment-emergent SAEs
- Treatment-emergent SAEs by causality (related/unrelated)

- Treatment-emergent SAEs leading to death
- TEAEs leading to withdrawal

Data listings will be provided for:

- All TEAEs sorted by patient number
- All TEAEs sorted by MedDRA SOC and PT
- SAEs
- Treatment-emergent SAEs
- Treatment-emergent SAEs leading to death

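### Protocol 9.2.1.1 makes a response pattern known from animals a criterion for both possibly and probably related, so a new human reaction can be graded down in the related-AE outputs

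*Protocol*

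**What the plan says.** Protocol 9.1.1 allows four grades of relationship and has no unassessable option. Protocol 9.2.1.1 defines them as follows.

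- *Unrelated*: "applicable to an AE that occurs when the subject was not exposed to study treatment or another cause is obvious".
- *Unlikely*: an event meeting two criteria, "Does not follow a reasonable temporal sequence from study drug dosing" and "May readily have been produced by the subject's clinical state, environmental, or toxic factors, or other therapy administered to the subject".
- *Possibly*: introduced as "applicable to AEs where connection with dosing of study drug appears unlikely but cannot be ruled out". Two bullets follow: reasonable timing, and "It follows a known pattern of response to study drug dosing (based on animal studies".
- *Probably*: introduced as a relation held with high certainty. Three bullets follow: reasonable timing, no other reasonable explanation, and the same animal-study pattern.

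No *and* or *or* joins the bullets under the last two grades.

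The protocol has human data of its own. Section 1.3 states: "Three non-serious and one serious infusion related reactions regarded as related to treatment have occurred in 114 subjects receiving imlifidase". Of the animal work, section 1.1 mentions repeat-dose toxicology in rabbit and dog and gives only the no-effect and lowest-effect dose levels.

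Three places use the grade or set a related standard. Protocol 9.2.5 requires a preliminary causality assessment in the first report of a serious event. Protocol 9.2.6 defines a suspected serious adverse reaction as "any SAE for which there is a reasonable possibility that the investigational product caused the AE". SAP 4.7.1 defines the related group as "Related TEAEs (TEAEs considered to be possibly or probably related to IMP as judged by the investigator".

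**The concern.** A causality scale should place every event somewhere, and should do so for the same reasons at every site. Here the two grades that make up the related group both ask for a pattern seen in animals. A reaction that appears for the first time in humans is the kind of event for which that evidence may not exist. Even a repeat of the infusion reactions that the protocol already regards as related counts as a known pattern, read literally, only if animals showed it too.

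The text for *possibly* also pulls in two directions. Its introduction describes a doubtful link, in nearly the same word as the grade below it, while its bullets ask for evidence in favour of a link.

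At stake is the related/unrelated split in the safety outputs. An investigator who applies the listed criteria strictly may settle on *unlikely* for a well-timed event with no other cause, and the event then leaves the related counts. Another investigator may choose *possibly* for the same event.

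**Working it through.** The plan states no figure on this point, so the check is a logical one.

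**One event against the four grades.** Take an exposed subject and an event with reasonable timing, no other cause and no animal precedent. Read the bullets as joint criteria.

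| Grade | Deciding criterion | Met? |
|---|---|---|
| Unrelated | Not exposed, or obvious other cause | No |
| Unlikely | Poor timing and another ready explanation | No, on both |
| Possibly | Timing and animal pattern | No, pattern absent |
| Probably | Timing, no other explanation, animal pattern | No, pattern absent |

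Result: 0 of 4 grades.

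**All combinations.** Use four yes/no features for an exposed subject: obvious other cause (O), reasonable timing (T), alternative explanation (A) and animal pattern (P). That gives 2^4 = 16 combinations. An obvious other cause implies an alternative explanation, so the 4 with O yes and A no are dropped, which leaves 12. The rules are:

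- Unrelated = O
- Unlikely = (not T) and A
- Possibly = T and P
- Probably = T and (not A) and P

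Of the 12, 4 fit no grade, 4 fit exactly one and 4 fit more than one. Two of the four that fit none are due to the animal criterion: good timing, no obvious other cause, no animal pattern, with or without an alternative explanation. The other two have poor timing and no alternative explanation, which is a separate gap.

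If instead any single bullet is enough for *possibly* and *probably*, no combination is left out, but 10 of 12 fit more than one grade. These are counts of logical cases, not of expected events, and they leave out the introductory sentences.

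**Adding the introductory sentences.** The one for *possibly* admits any link that cannot be excluded, and the event above qualifies. The one for *probably* sets a high bar and does not waive the animal pattern. So *possibly* is reachable through its introduction alone, and *probably* is not reachable.

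**Outputs affected.** SAP 4.7.1 and section 8 use the related split in two overview rows (related TEAEs, related serious TEAEs) and in Tables 14.3.3, 14.3.5, 14.3.7 and 14.3.9: 2 + 4 = 6.

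**Size per event.** With 20 imlifidase subjects, regrading the only related event of one subject changes the percentage with a related TEAE by 1/20 = 5 points.

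**How often.** The documents give no rate for new reactions. For the known infusion reactions alone, assume four different subjects and the same rate here: 4/114 = 3.5%, and the chance of at least one in 20 subjects is 1 - (1 - 4/114)^20 = 0.51. Whether those reactions have an animal precedent is not stated, so this shows only that the criterion could well be put to use.

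**Against 9.2.6.** That section asks for a reasonable possibility and has no animal condition. An event can meet it and still meet none of the listed criteria sets in 9.2.1.1.

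**The case against.** The strongest reply is that the gap rests on an implied *and*, and that the introduction to *possibly* already catches the event. This stands in part: a sensible investigator can choose *possibly*. To do so, the investigator must set the listed bullets aside and accept a description of the link as doubtful. Sites may differ in that, and *probably* remains closed.

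A reader might infer that the trial's safety signals are unreliable. The documents do not support that:

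- All serious events are reported whatever their causality (protocol 9.2.5).
- Expedited reporting has its own, broader causality test, and unexpectedness is judged against the reference safety information, not against animal findings (9.2.6).
- The Safety Review Committee looks at both arms (3.1.2).
- All TEAEs and all SAEs are tabulated regardless of grade (SAP 4.7.1).

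SAP 4.1.4 also sets a missing causality to related, so an event left ungraded is not lost. That protects blanks only. Causality is recorded for every event (protocol 9.2.1), so the realistic error is a wrong grade.

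A reader might also infer that timing alone would make most early events both possibly and probably related. That fails too: *probably* asks for high certainty, and the SAP pools the two grades. The clash between *possibly* and *unlikely* is largely verbal, because their timing criteria are opposite.

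Finally, nothing shows that any event was misgraded. The animal findings are not described, so nobody can say from these documents which human reactions lack a precedent.

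**Conclusion.** The definitions are wrong as written, with low to moderate severity. The effect is confined to the six related outputs and to the preliminary causality in the first report of a serious event, where a misfitting grade could enter triage. All analyses are descriptive, and no efficacy result or planned number changes.

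The conclusion assumes that the bullets are read together, that one of the four grades is recorded, and that some reactions in this trial have no animal counterpart. The first is the more natural reading, since the alternative leaves most combinations in several grades at once. The third cannot be checked from the documents. The supported claim is that a new human reaction can be under-graded or graded inconsistently between sites, not that this has happened.

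**What to change.** Amend protocol 9.2.1.1:

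- *Possibly*: delete the words describing the link as appearing unlikely. Keep reasonable timing and a link that cannot be excluded.
- *Probably*: keep reasonable timing and the absence of another reasonable explanation.
- Both: replace the animal-study restriction with a known pattern from human or nonclinical data, and state that it supports the grade but is not required.
- State how the bullets combine, and align the scale with the causality standard in 9.2.6.

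Keep the SAP grouping of *possibly* plus *probably* as related, and its rule for missing causality.

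The cost is a wording amendment and a note to sites, with no new visits or data. The drawback is timing. An expected start in January to March 2019 plus 35 months of recruitment runs to December 2021 to February 2022. Six months of follow-up then takes it to June to August 2022, and the two SAP versions are dated June and August 2022. On that timetable most events may already be graded. A one-off causality confirmation before database lock may be needed, and in an open-label study it would be made with treatment known and could itself introduce bias. Keep both the grade as recorded and any revised grade, and document each change and its reason.
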